Study background (with bibliographic references)	
Kidney transplantation is currently the reference treatment for end-stage kidney disease, with more than 170,000 transplants performed worldwide each year (Global Observatory on Donation and Transplantation, 2024). Despite major progress in short-term survival, long-term graft survival remains limited: approximately 40% of patients return to dialysis within 10 to 15 years after transplantation (Hart et al, AJT 2019, PMID 30838768).
 
In recent years, artificial intelligence (AI) has emerged as a promising tool to predict graft outcomes and support clinical decision-making (Raynaud et al, Lancet Digital Health 2021 PMID 34756569; Loupy et al, Nature Medicine 2025 PMID 40659768). The iBox system, developed by the Paris Institute for Transplantation and Organ Regeneration, makes it possible to calculate a personalized probability of graft loss up to ten years after the evaluation of a kidney transplant recipient.
 
This algorithm has been internationally validated in several cohorts and clinical trials (Lombardi et al, AJT 2025, PMID 39674514; Truchot et al, JASN 2025, PMID 40168162), performs better than clinicians in predicting risk (Divard et al, Communications Medicine 2022, PMID 36418380), and was qualified by the European Medicines Agency as an endpoint for clinical trials in 2022.
 
However, although the clinical value of iBox and similar predictive tools is well documented, how patients perceive them remains largely unexplored.
 
Understanding how kidney transplant recipients perceive the prediction of their individual risk of graft loss (in terms of usefulness, acceptability, fears, or impact on daily life), as well as their broader views on the role of artificial intelligence in medicine, including their hopes, expectations, and concerns regarding its deployment, is essential to ensure implementation that is ethical, transparent, and truly patient-centered (Young et al, Lancet Digital Health 2021, PMID 34446266).

Primary objective and corresponding endpoints (Please specify the longer-term application of the study if necessary)	This study therefore aims to explore the perceptions, expectations, and concerns of kidney transplant recipients regarding the use of artificial intelligence, and to assess their specific perceptions of the use of a graft loss risk prediction system, through an open-ended questionnaire distributed on a large scale in France and the United States.
Secondary objectives and corresponding endpoints	--
Study period (Please specify what justifies it)	May 2026: Distribution of the questionnaire to the collaborating transplant centers and patient associations. June 2026: Data collection and management. July 2026: Analysis of the results. September 2026: Presentation and discussion of the results with the participating centers/associations. October 2026: Publication
Number of participants (Please specify what justifies it)	The investigators plan to distribute the questionnaire to a sample of between 10,000 and 20,000 kidney transplant recipients. Based on response rates observed in comparable studies using patient questionnaires, an estimated response rate of between 10% and 15% is expected, which would provide a sufficient volume of responses to ensure statistical robustness and diversity of represented profiles.
Inclusion criteria	age \geq 18 years proficiency in French or English electronic consent provided
Exclusion criteria	severe cognitive impairment preventing understanding technical inability to access the questionnaire

Type of study (Monocentric or multicentric, qualitative, quantitative, mixed, practice study, reuse of data collected during care, use of biological samples, etc.)
	
International multicenter cross-sectional survey conducted using an anonymous online questionnaire.
 
The study adopts a mixed-methods approach, combining qualitative and quantitative analysis of responses. No medical or biological data will be used, and there will be no reuse of data collected during care.

Does this study fall within the scope of a care team?
	
No


Summary methodology (What statistical analysis strategy, what type of interview, what mode of observation, etc.)
	
Collaboration with transplant centers and patient associations: The investigators' team is highly collaborative and has a broad international network of clinical and patient-association partners in the field of kidney transplantation. This network, built over the course of the investigators' research and previous collaborations, will be mobilized for the present study.
 
The investigators have already obtained preliminary agreement from three French kidney transplant centers, as well as five patient associations (including France Rein and Le Flambeau de la Vie in France, and The Voice of the Patient and the American Association of Kidney Patients in the United States). These partners will play a key role in disseminating the questionnaire to kidney transplant recipients and in representing the patient perspective.
 
Questionnaire development: The questionnaire was developed based on a literature review on patients' perceptions of artificial intelligence and predictive medicine (Erul et al, Cancer Control 2025, PMID 40407404; Fritsch et al, Digital Health 2022, PMID 35983102).
 
The questionnaire was co-designed and tested with six kidney transplant recipients (French and American), allowing us to refine the wording of the questions and validate the bilingual French-English translation. The questionnaire is implemented via the secure REDCap interface (GDPR-compliant). Each participant receives a personal code allowing them to return and modify their responses before final validation (questionnaire presented in the appendix to this document).
 
Questionnaire distribution: Dissemination will take place through partner patient associations and collaborating transplant centers in France and the United States. The questionnaire will be distributed via a secure and anonymous REDCap platform hosted on institutional servers that comply with data protection standards (GDPR). Participants will receive a unique link providing direct access to the online questionnaire. They will be able to respond independently, at their own pace, and may interrupt their participation at any time without justification or consequence.

	
Data analysis: The responses collected will be analyzed using a quantitative approach. Qualitative analyses will rely on thematic analysis assisted by Large Language Models (LLMs). These models will make it possible to automatically extract recurring themes, associated emotions, and nuances of perception in free-text responses, according to a standardized methodology developed by the investigators' team. The investigators have already successfully conducted this type of LLM-based thematic analysis (Raynaud et al, PsyArxiv 2025 https://osf.io/preprints/psyarxiv/pnx9e_v1).
 
Analyses will be conducted via commercial language-model APIs (Anthropic Claude, OpenAI ChatGPT, xAI Grok), justified by their superior performance for multilingual qualitative analysis. Only pseudonymized text responses will be transmitted, with no identifiers or sociodemographic data. Providers contractually guarantee zero data retention. Participants will be asked not to mention identifying information in their free-text responses (see the information notice in the appendix to this document).
 
To ensure reliability and scientific rigor, systematic manual verification will be performed on a representative subsample of responses. This independent review will make it possible to compare human and automated coding and refine the thematic categories.
 
Originality of the study: Unlike the vast majority of surveys conducted with patients, the questionnaire will contain only open-ended questions, giving each patient the opportunity to express themselves freely and in a nuanced way about their perceptions and feelings.
 
Such an approach, previously difficult to implement on a large scale, is now made possible by language models (LLMs), which are able to finely analyze large sets of textual responses.
 
This innovative methodology will provide a more faithful, precise, and human understanding of patients' perspectives, paving the way for a new generation of studies centered on patients' lived experience and voice.

Data collected (Justify the collection of sensitive/identifying data, if applicable)
	
 • Age • Sex • Year of the last transplant • Country of the last transplant • Transplant follow-up center • Transplant rank • Current occupation or last occupation held • Perceptions of the role of AI in medicine • Perceptions regarding a graft loss risk prediction system


Data flow (What happens to the data from extraction until deletion? Collection software, storage, security of storage media, access, partner recipients or subcontractors, retention period, etc.)
	
Data will be collected through the REDCap platform (HDS-certified hosting on Google Cloud, GDPR-compliant). The questionnaire is anonymous: no nominative data or identifiable medical data will be collected. Each participant will receive a unique link generating a non-traceable alphanumeric identifier.
 
The data flow is as follows:
 
Dissemination: Partner transplant centers and patient associations disseminate the REDCap link to eligible patients.
 
Collection: Participants complete the questionnaire anonymously via REDCap.
 
Export: Pseudonymized data are extracted (CSV format) by authorized members ([name], [name], [name]).
 
Storage: Files are stored in encrypted form on the secure PARCC INSERM U970 server, with access controlled by secure authentication.
 
Qualitative analysis by LLM: Only textual responses (without identifiers, sociodemographic data, or transplant-related information) are transmitted via secure API (HTTPS/TLS) to language-model providers (zero data retention). Results are returned to the PARCC INSERM server. Quantitative analyses are performed locally using R.
 
Archiving: 3 years in the active database, then 20 years in archives, under the responsibility of [name].
 
Fully anonymized datasets may be archived for secondary research purposes or scientific replicability.


Participant information (For example: recruitment during a consultation, or patients recontacted by mail, or call on social networks, etc. Attach the information notices planned for the different types of participants: adults, adolescents, children, legal guardians, etc. Justify the absence of an information
	
Participants will be contacted by email via their follow-up center, using the existing contact databases available in these centers.
 
The invitation message will briefly present the study and its sponsor, the Paris Institute for Transplantation and Organ Regeneration, as well as the responsible researchers.
 
It will also include an information notice specifying the objectives of the study, confidentiality arrangements, and a direct link to the online questionnaire hosted on REDCap.
 
Participation will be entirely voluntary, with no impact on medical follow-up or on the relationship with the transplant team.

notice, applicable.)	if	
Legal entity responsible for the project		INSERM
Natural person responsible for the project		[name]

Questionnaire: Perceptions of kidney transplant recipients about the role of Artificial Intelligence (AI) in healthcare and about a graft failure prediction system

1. Purpose of the study

You are invited to participate in a study aimed at better understanding how kidney transplant recipients perceive the use of a prediction system based on artificial intelligence (AI) that can predict the probability of graft loss (return to dialysis or retransplantation) over time. We also wish to gather patients' opinions on the future role of AI in medicine. The purpose of this study is to better understand how transplant recipients experience the arrival of new technologies such as artificial intelligence in their medical follow-up.

2. Consent Form

Your participation involves completing an anonymous questionnaire of approximately 15 to 20 minutes. No identifiable personal data will be collected. You may stop at any time, without justification.

By ticking the box below, you consent to participate in this study.

☐ Yes, I agree to participate in this study

☐ No, I do not wish to participate

3. Explanation of the prediction system

The prediction system was developed to help physicians and patients assess the health of the kidney graft. It combines several clinical data points (kidney function, histological results, and immunological results) and predicts the percentage of risk that a patient will lose their graft over the next 10 years. The goal of this prediction system is to improve clinical decision-making, as well as the discussion between the physician and the patient.

A. Have you ever heard of this type of prediction system?

B. If yes, does your physician use such a prediction system in your post-transplant follow-up? Do you have access to the predictions?

4. Questions specific to the prediction system

- A. What do you think of the idea that an artificial intelligence such as this prediction system could predict your personal risk of graft loss?
- B. Do you find it useful for your physician to have access to this information? Why?
- C. Would you personally want to know your graft loss prediction?
- D. What fears or concerns do you have about AI being used to predict the outcome of your transplant?
- E. How could this information influence your daily life, for example your personal, family, professional choices, or your leisure activities?

5. General questions about artificial intelligence in healthcare

- A. In general, what do you think about the use of artificial intelligence in today's healthcare?
- B. What hopes or expectations do you have regarding AI in healthcare?
- C. What fears or reservations do you have regarding AI in healthcare?
- D. In your opinion, in what situations should or should not AI be used?
- E. Would you like to add any comments about your feelings regarding this prediction system or AI in medicine?

6. General information (demographics)

Age: _____ (years)

Sex: ☐ Female ☐ Male

Year of last transplant: _____

Country of transplant: _____

Transplant follow-up center: _____

Transplant rank: ☐ First ☐ Second ☐ Third or more

Current occupation or last occupation held: _____

7. Our thanks

Thank you for taking the time to share your perspective. Your responses will help us better understand the role that patients wish to give to artificial intelligence in the medicine of tomorrow. Your transplant center (or your patient association) will share the results of the study with you once the analyses are completed.

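### The eligibility criteria and questionnaire never establish that a respondent has had a kidney transplant or whether the graft still works, so people outside the target population can enter

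*Protocol*

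**What the plan says.** The primary objective is to "explore the perceptions, expectations, and concerns of kidney transplant recipients regarding the use of artificial intelligence". The row on the number of participants plans to "distribute the questionnaire to a sample of between 10,000 and 20,000 kidney transplant recipients" and adds that "an estimated response rate of between 10% and 15% is expected". The population is therefore named clearly.

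The operative criteria do not carry that definition. The inclusion row lists an age of at least 18 and "proficiency in French or English electronic consent provided". The exclusion row lists "severe cognitive impairment preventing understanding technical inability to access the questionnaire". Neither mentions a transplant.

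Distribution has two routes. Under Summary methodology and Data flow, both transplant centers and patient associations pass on the link. The associations include two in France "and The Voice of the Patient and the American Association of Kidney Patients in the United States". The Participant information row describes only email contact through the follow-up center.

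In the questionnaire, the consent box records agreement to take part and nothing else. Section 4, item A asks about an AI that "could predict your personal risk of graft loss". Transplant items appear only in section 6: year of last transplant, "Country of transplant", follow-up center and rank (first, second, third or more).

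**The concern.** The trait that defines the study population is missing from the list that decides who is eligible. Data flow sends the link to eligible patients, which leads back to the same incomplete list. The association route matters most, because the protocol does not describe those memberships as limited to transplant recipients, and a kidney-patient association may also include people on dialysis or awaiting a transplant.

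Two things are at stake. One is whether the reported views are those of kidney transplant recipients. The other is whether section 4 can be interpreted, since a question about one's own risk of losing the graft means something different to a person whose graft has already failed. Both depend on information that is not collected. The protocol uses no medical data, and the identifier is non-traceable, so status cannot be checked against records afterwards.

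**Working it through.** **1. Does any step establish transplant status?**

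- *Inclusion and exclusion criteria:* age, language, consent, cognition and technical access. No transplant criterion.
- *Consent (questionnaire section 2):* agreement only.
- *Sections 3 to 5:* 2 + 5 + 5 = 12 questions, none asking whether the respondent has a kidney transplant.
- *Section 6:* year, country, center and rank. The organ is not named, there is no answer for someone never transplanted, and current graft function is not asked.

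**2. What could be recovered from the fixed items?**

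- *Never transplanted:* no truthful answer to year or rank, so a blank is a clue. A recipient who skips these items leaves the same blank, so the identification is indirect.
- *Another organ:* can answer year, country, center and rank truthfully, and so looks the same as a kidney recipient.
- *Failed kidney graft:* answers exactly as a recipient with a working graft does. The Study background gives about 40% returning to dialysis within 10 to 15 years, so some such respondents should be expected.

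**3. Implied number of responses.** The protocol states no target number of respondents. From its figures, 10,000 × 0.10 = 1,000 at the low end and 20,000 × 0.15 = 3,000 at the high end.

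**4. Sampling error, for scale.** The 95% half-width for a proportion of 50% is 1.96 × √(0.25/n):

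- n = 1,000: 1.96 × 0.0158 = 3.1 points
- n = 3,000: 1.96 × 0.0091 = 1.8 points

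**5. Possible shift.** Let e be the share of respondents who are not kidney transplant recipients, and d the difference between them and recipients in the percentage giving a particular answer. The pooled percentage then shifts by e × d. The protocol gives neither quantity, so both are assumed over a range:

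| e | d = 10 points | d = 20 points |
|---|---|---|
| 5% | 0.5 | 1.0 |
| 10% | 1.0 | 2.0 |
| 20% | 2.0 | 4.0 |
| 30% | 3.0 | 6.0 |

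**6. When the shift reaches the half-width.** With d = 20, this needs e of about 1.8/20 = 9% at n = 3,000, or 3.1/20 = 15.5% at n = 1,000. With d = 10, it needs 18% or 31%. More responses narrow the half-width but leave the shift unchanged.

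**The case against.** The strongest reply is that the intended population is plain throughout. The objective, the sample statement and the account of the partners' role all name kidney transplant recipients, and the questionnaire's title and purpose tell every reader whom it is for. On the center route, the mailing list is itself a filter. This stands, and it limits the claim: others can enter, but nothing shows that they will or in what number. A reader might infer that dialysis or pre-transplant patients will make up a material part of the sample. The documents do not support that, because they say nothing about the composition of the associations' lists.

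A reader might also count failed-graft respondents as ineligible. They are not. They have received a kidney transplant, and the objective does not require a working graft. The weakness is that section 4 presupposes one and the data cannot separate the two groups.

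A third tempting inference is that anonymity makes every ineligible record impossible to remove. Removal needs the content of a record, not the person's identity. Blank year or rank points to a never-transplanted respondent, and country and center allow some selection by place. The difficulty remains for other-organ recipients, and for telling a non-recipient's blank from a skipped item.

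The analysed set and the handling of partial questionnaires may properly be left to a statistical analysis plan, so their absence here is not criticised. But no analysis plan can select on organ or graft status if neither is collected. The invitation's information notice might also state who should take part. Such wording would help, but it would not put graft status into the data.

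Finally, the study is exploratory and states no precision target. That is fair, and the comparison with sampling error is only a yardstick.

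**Conclusion.** The point holds as a gap in eligibility and data capture. The criteria omit the defining trait, no questionnaire item supplies it, and the association route gives people outside the population a way in. Separately, section 4 will pool respondents with working and failed grafts without any means of telling them apart.

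The size of any bias is unknown. Over the assumed ranges (5% to 30% non-recipients, 10 to 20 points of difference) it runs from 0.5 to 6 points. It is therefore negligible at one end and larger than sampling error at the other. The gap itself rests on no assumption; it follows from the criteria and the questionnaire as written. It should be fixed before distribution, because the missing items cannot be recovered once anonymous responses are in. It does not invalidate the design.

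**What to change.** - Add to the inclusion criteria: has received a kidney transplant.
- Directly after consent, add two tick-box items: (1) *Have you received a kidney transplant?* (Yes / No, where No ends the questionnaire); (2) *Is your most recent kidney graft working today?* (Yes / No / Unsure).
- Report section 4 by graft status, keeping failed-graft respondents in the study.

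The cost is one line in the criteria, two items in REDCap, under a minute of each respondent's time and a slightly smaller analysed number.

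### Patients can be invited through both a center and an association, and nothing in the questionnaire prevents or links two entries by one person; the likely effect is modest

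*Protocol*

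**What the plan says.** **Who sends the invitation.** Summary methodology: "Dissemination will take place through partner patient associations and collaborating transplant centers in France and the United States". Data flow agrees: "Partner transplant centers and patient associations disseminate the REDCap link to eligible patients". The closing text of the questionnaire also allows for either source, since it says that the center or the association will return the results. Participant information gives a narrower route: "Participants will be contacted by email via their follow-up center, using the existing contact databases available in these centers". Associations do not appear there. The agreements reported so far are "preliminary agreement from three French kidney transplant centers, as well as five patient associations".

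**What link is sent.** Summary methodology promises each participant a unique link, and so does Data flow: "Each participant will receive a unique link generating a non-traceable alphanumeric identifier". The Dissemination line of Data flow refers simply to the REDCap link, and Participant information to "a direct link to the online questionnaire hosted on REDCap". No section says who issues the unique links or whether mailing lists are compared.

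**What ties entries together.** Summary methodology: "Each participant receives a personal code allowing them to return and modify their responses before final validation". Data flow: "The questionnaire is anonymous: no nominative data or identifiable medical data will be collected". The demographic items are age, sex, year and country of last transplant, follow-up center, transplant rank and occupation. The questionnaire as printed has no item on earlier participation and no instruction to answer only once.

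**The concern.** A transplant recipient who belongs to a partner association may also be followed at a partner center, and with five associations some patients may belong to two. Links that are unique per invitation do not stop such a person from entering twice. The code lets someone return to one entry before validating it; it does not join two invitations.

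The duplicates would come from patients in both networks, who may be more engaged than others. Any theme frequency would lean toward their views, and the number of records would exceed the number of people. This matters because the section on the number of participants rests its claim of robustness on the volume of responses. A later analysis plan cannot fully repair the gap: once anonymous collection has closed, nobody can be asked whether they answered before.

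**Working it through.** **Inputs from the protocol.** Recipients to be reached: N = 10,000 to 20,000. Response rate: r = 10% to 15%. Implied responses: 10,000 × 0.10 = 1,000 up to 20,000 × 0.15 = 3,000. The protocol gives no overlap, precision target or planned interval, so it has no figure of its own to reproduce.

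**Assumptions.** A share o of the N people receive exactly two invitations. Each invitation is answered independently with probability r.

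**Formulas.**
- Second records = o × N × r².
- Total records = N × r × (1 + o), so the share that are second records is s = o × r / (1 + o).
- Fraction of respondents who answer twice: d = o × r / (1 + o − o × r).

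| Overlap o | N = 10,000, r = 10%: second records; s; d | N = 20,000, r = 15%: second records; s; d |
|---|---|---|
| 5% | 5; 0.5%; 0.5% | 22.5; 0.7%; 0.7% |
| 20% | 20; 1.7%; 1.7% | 90; 2.5%; 2.6% |
| 50% | 50; 3.3%; 3.4% | 225; 5.0%; 5.3% |
| 100% | 100; 5.0%; 5.3% | 450; 7.5%; 8.1% |

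Check of the last row: d = 0.01 / 0.19 = 5.3% and 0.0225 / 0.2775 = 8.1%.

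**Reported number.** Records exceed people by the factor 1 + d. At full overlap this is 2,000 records from 1,900 people, or 6,000 records from 5,550 people.

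**Theme frequency.** Double responders should carry weight d but carry 2d / (1 + d). A theme frequency therefore shifts by d(1 − d) / (1 + d) times the gap in prevalence between double responders and the rest. At d = 5.3% the multiplier is 0.047, and at d = 8.1% it is 0.069. Even with full overlap, about 5% to 7% of that gap enters the estimate.

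**Precision, for scale only.** If second records repeat the first answers exactly, the variance of a proportion grows by 1 + 2s. At s = 5%, the 95% half-width for a proportion of 0.5 goes from 3.10 to 3.25 points at 1,000 records, and from 1.79 to 1.88 points at 3,000. Actual coverage of a nominal 95% interval is then 93.8%.

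**How well matching could work.** Chance pairs = n(n − 1)/2 divided by the product of the effective numbers of categories. The category counts are assumed: age 40 to 50, sex 2, transplant year 12 to 15, center and country together 5 to 10, rank 1.4. The products are 40 × 2 × 12 × 5 × 1.4 = 6,720 and 50 × 2 × 15 × 10 × 1.4 = 21,000.
- n = 1,000: 499,500 pairs, giving 24 to 74 chance matches.
- n = 3,000: 4,498,500 pairs, giving 214 to 669.
- With occupation added at an assumed 30 or 8 effective categories: 23.8/30 = 0.8 to 74.3/8 = 9.3 at n = 1,000, and 214.2/30 = 7.1 to 669.4/8 = 83.7 at n = 3,000.

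Without occupation, chance matches are about as many as the plausible true duplicates, or more. With occupation, the flag is useful but still not proof.

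**The case against.** Several points on the other side are sound.

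- **Detectability.** A reader might infer that duplicates cannot be found at all. The protocol collects seven demographic fields and long free-text answers, and Data flow withholds the demographics only from the language-model providers. Probable duplicates can be flagged locally.
- **Counting.** A reader might infer that every submission will be counted as a different person. The protocol states no counting rule, and a rule for cleaning duplicates may sit in a plan that is not shown.
- **Link.** A reader might infer one shared, reusable link. No section says so. The looser references to a link are compatible with the unique link promised twice.
- **Contact route.** On the text of Participant information alone, overlap between centers and associations would not arise. That is a reason to reconcile the sections, not to dismiss the point. The only centers reported as agreed so far are French, so this route alone would not yet reach patients in the United States.
- **Invitation text.** The information notice and invitation message are not shown in full, and an answer-once line could be there.
- **Harms.** No interval is planned that could be too narrow. The response rate is not necessarily overstated, because a second invitation can also enter the denominator.
- **Burden.** A form of 15 to 20 minutes discourages a second completion.

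What remains is the two-channel dissemination, the absence of any link between two entries, and a questionnaire without a screening item or instruction.

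**Conclusion.** The point holds as a modest data-quality gap. The sections on dissemination disagree about who invites patients. Where both channels are used, one person can enter twice and only a probabilistic match would show it.

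If two invitations are answered independently at 10% to 15%, d runs from about 0.5% at 5% overlap to 5.3% to 8.1% at full overlap. Having 10% or 20% of people answer twice would need strong positive dependence between the two responses, or more than two invitations for many patients. Nothing in the protocol supports such figures. Independence is itself an assumption: engaged patients may reply more readily to both invitations, so 8.1% is a guide and not a hard limit. The likely consequences are a slightly inflated number of participants and a small tilt in theme frequencies. The point is worth acting on because the preventive step is nearly free and must come before distribution.

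**What to change.** 1. Reconcile Summary methodology, Data flow and Participant information. State whether associations invite patients directly, who issues the unique links, and use one description of the link throughout.
2. Add to the opening page of the questionnaire: *Have you already completed this questionnaire? (Yes = end)* and *If you received this invitation more than once, please answer only once.*
3. Flag records that agree on age, sex, transplant year, country, center, rank and occupation. Confirm each flagged pair against its free text, locally, so that demographics still do not reach the language-model providers.
4. Repeat the results without the confirmed duplicates as a sensitivity check. Do not delete records on a demographic match alone, since chance matches would remove real people.

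The cost is one extra item, one sentence, a short local check in R on fields already collected, some reading of flagged pairs, and a slightly smaller reported number. Anonymity is unaffected.
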